CTEP	Cancer Therapy Evaluation Program
DHHS	Department of Health and Human Services
DILI	Drug Induce Liver Injury
DNA	Deoxyribonucleic Acid
DTC	Differentiated Thyroid Cancer
ECG	Electrocardiogram
ECOG	Eastern Cooperative Oncology Group
eCRF	Electronic Case Report Form
ERK	Extracellular Signal-Related Kinase
FDA	Food and Drug Administration
FDAAA	Food and Drug Administration Amendments Act
FDAMA	Food and Drug Administration Modernization Act
GCP	Good Clinical Practice
GFR	Glomerular Filtration Rate
HCC	Hepatocellular Carcinoma
HIPAA	Health Insurance Portability and Accounting Act
HRI	HonorHealth Research Institute
ICF	Informed Consent Form
ICH	International Conference of Harmonization
INR	International Normalized Ratio
IRB	Institutional Review Board
IV	Intravenous

KRAS	KRAS gene
LDH	Lactate Dehydrogenase
MRI	Magnetic Resonance Imaging
NCI	National Cancer Institute
NS	Normal Saline
OS	Overall Survival
PD	Progressive Disease
PDA	Pancreatic Ductal Adenocarcinoma
PFS	Progression free survival
P-gp	P-glycoprotein
PO	By mouth (from Latin "per os")
PR	Partial Response
pRBC	Packed Red Blood Cells
PT	Prothrombin Time
RCC	Renal Cell Carcinoma
RECIST	Response Evaluation Criteria in Solid Tumors
SAE	Serious Adverse Event
SPF	Sun Protection Factor
SD	Stable Disease
TGen	Translation Genomics Research Institute
ULN	Upper Limit of Normal
UVA	Ultraviolet A
UVB	Ultraviolet B
WOCBP	Women of Childbearing Potential

TRIAL SCHEM

Patients with metastatic advanced RAS mutated refractory pancreatic cancer where the patient has progressed on ≥ 2 prior chemotherapy regimens for their advanced disease.

[figure not shown]

Vemurafenib
480 mg PO BID daily*
+
Sorafenib
200 mg PO AM and
200 mg PO PM
daily**

X 28 days
(1 cycle)

Tumor Assessment
every 8 weeks + CA19
9 (or CA 125, or CEA if
not expressers of CA
19-9)

Study treatment continues until disease progression or unacceptable toxicity

Key Study Endpoints:

- Disease control rate (DCR)- CR+PR+SD at 16 weeks
- Safety
- Progression Free Survival (PFS)
- Overall Survival (OS)
- Changes in plasma free DNA mutated KRAS – Blood collected at baseline and prior to each cycle (X)

*Vemurafenib Dose level 1 will be 240 mg PO BID

** Sorafenib Dose level 1 will be 200 mg PO daily

TRIAL SYNOPSIS


Title and Number: A Phase II Trial of Vemurafenib in Combination with Sorafenib to Treat Patients With Advanced KRAS Mutated Pancreatic Cancer. Targeting RAF Dimers to Suppress Oncogenic RAS Signaling (The [name] Study) Protocol No. HRI-Vemurafenib-Sorafenib-001 Version 2.0 dated 14 Oct 2021

Sponsor: HonorHealth Research Institute

Principal Investigator: [name], MS – HonorHealth Research Institute, Scottsdale, AZ

Consulting Investigator: [name] [name], FACP, FASCO, FAACR – HonorHealth Research Institute, Scottsdale, AZ and Translational Genomics Research Institute (TGen), an Affiliate of City of Hope [name] – Sheba Medical Center, Israel

Clinical Phase: Phase II

Objectives:
 
Primary: To determine the efficacy by the disease control rate (CR+ PR +Stable at 16 weeks) of the combination of the type I½ RAF inhibitor (RAFi) Vemurafenib in combination with the type II RAFi Sorafenib in patients with KRAS mutated refractory pancreatic cancer. Note: Type I inhibitors bind to the active protein kinase conformation (DFG-ASP “in” αC helix “in”). Type I½ inhibitors bind to a DFG-ASP “in” and αC helix “out” inactive conformation. Type II RAF inhibitors trap kinases in the DFG-ASP “out” αC helix “in” inactive conformation (Roskowsky, 2016, Rukhlenko 2018).
 
Secondary:
 
 1. To confirm the safety of giving Vemurafenib + Sorafenib to patients with advanced pancreatic cancer 2. To determine the clinical activity of Vemurafenib + Sorafenib as defined progression free survival (PFS) and overall survival (OS) rate. 3. To utilize circulating tumor DNA (ct DNA) in plasma to give qualitative (mutations) and to some extent quantitative (amount of ct DNA) information regarding BRAF and KRAS. This will be measure at baseline and just before each cycle. 4. To measure phospho ERK and phospho AKT in plasma to determine if the treatment has hit the intended target (Takano et al. 2010, Petricoin 2009). This will be measure at baseline and just before each cycle

Exploratory: 
 To evaluate changes in phospho ERK and phospho AKT in tumor tissue.
Trial Design: Open Label, Single Arm Trial
Number of Patients: Between 7 and 12 evaluable patients In the first stage 7 evaluable patients will be accrued. If there are zero patients with disease control (CR+ PR +Stable at 16 weeks) in these first 7 evaluable patients, the study will be stopped. Otherwise, 5 additional evaluable patients will be accrued for a total of 12 evaluable patients. An evaluable patient is defined as one that receives any number of doses of both agents (Vemurafenib + Sorafenib) and has a scan after at least 2 cycles of treatment.
Name & Dose of Drugs: 
 Vemurafenib will be given 480 mg PO BID daily x 28 days = 1 cycle Dose level -1 will be 240 mg PO BID Sorafenib will be given 200 mg PO BID daily x 28 days = 1 cycle (Dose level -1 will be 200 mg PO daily) 
Note: All doses are to be taken without food. Doses can only be taken one hour before or 2 hours after a meal.

Patient Population: Patients with metastatic advanced KRAS mutated refractory pancreatic cancer where the patient has progressed on ≥ 2 prior chemotherapy regimens for their advanced disease.
Endpoints: Primary: disease control rate (defined as CR + PR + Stable at 16 weeks) using RECIST 1.1 criteria. Secondary: 
 Safety of giving vemurafenib + sorafenib in this population of patients Progression free survival (PFS) Overall survival (OS) Identify whether or not the drug combination resulted in changes in plasma free DNA mutated KRAS, BRAF, phospho ERK and phospho AKT 
Exploratory:
 
 Changes in phospho ERK and phospho AKT in tumor tissue.
Inclusion Criteria: 
 Be able to understand and be willing to sign the written informed consent for the trial. A signed informed consent form must be appropriately obtained prior to the conduct of any trial-specific procedure.

2. Be ≥ 18 years of age on day of signing informed consent.
3. Histologically confirmed cancer of the pancreas (KRAS mutated) with metastases and progression on at least ≥ 2 prior treatment regimens for their disease.
4. Known mutation status of KRAS and BRAF kinases. For those patients in which this has not previously been determined, the patient must have an archival tumor specimen (primary or metastatic site) available to submit to confirm KRAS and BRAF status.
5. Have a performance status of 0 or 1 on the ECOG performance scale.
6. Demonstrate adequate organ function as defined below:
 - a. Absolute neutrophil count $\geq 1,500/\text{mm}^3$
 - b. Platelet concentration $\geq 60 \times 10^9/\text{L}$
 - c. Hemoglobin $\geq 8.5 \text{ g/dL}$. Criteria must be met without erythropoietin dependency and without packed red blood cells (pRBC) transfusion within the last 2 weeks.
 - d. Serum creatinine $< 1.5 \times$ institutional ULN.
 - e. Total bilirubin $\leq 2.5 \text{ mg/dL}$
 - f. Alanine aminotransferase (ALT) and Aspartate aminotransferase (AST) $< 5 \times$ ULN
 - g. Prothrombin time (PT) ≤ 60 seconds or International Normalized Ratio (INR) ≤ 2.3
7. Female participants of childbearing potential must have a negative serum pregnancy test performed within 24 hours prior to receiving first dose of trial medication. Post-menopausal women (defined as no menses for at least 1 year) and surgically sterilized women are not required to undergo a pregnancy test.
8. A female participant is eligible to participate if she is not pregnant, not breastfeeding, and at least one of the following conditions applies:
 - a. Not a woman of childbearing potential (WOCBP)
 - OR
 - b. A WOCBP who agrees to follow the contraceptive guidance during the treatment period and for at least 30 days after the last dose of trial treatment.
9. Male participants must agree to use contraception during the treatment period and for at least 30 days after the last dose of trial treatment and refrain from donating sperm during this period.
10. Patient must have QTC of $\leq 500\text{ms}$.
11. Subject must be able to swallow and retain oral medication.
12. **Measurable disease per RECIST 1.1**

Exclusion Criteria:

1. Is currently participating and receiving trial therapy or has participated in a trial of an investigational agent and received trial therapy or used an investigational device within 2 weeks of the first dose of this trial's treatment.
2. Has had prior chemotherapy, targeted small molecule therapy, or radiation therapy within 2 weeks prior to Cycle 1/Day 1 or who has not recovered (i.e.

NCI-CTC AE Version 5.0 \leq Grade 1 at the time of signing informed consent) from adverse events due to a previously administered agent(s).

Note: Patients with \leq Grade 2 neuropathy and \leq Grade 2 alopecia are an exception to this criterion and may qualify for the trial.

3. Previous BRAF inhibitor use such as vemurafenib, GSK2118436 or sorafenib.
4. If patient received major surgery, and has not yet recovered adequately from the toxicity and/or complications from the intervention prior to starting therapy.
5. Previously untreated or concurrent cancer that is distinct in primary site or histology from pancreatic cancer except cervical cancer in-situ, treated basal cell carcinoma, or superficial bladder tumor. Subjects surviving a cancer that was curatively treated and without evidence of disease for more than 3 years before study entry. All cancer treatments must be completed at least 3 years prior to study entry (i.e., signature date of the informed consent form).
6. Has known active central nervous system (CNS) metastases and/or carcinomatous meningitis. Patients with previously treated brain metastases may participate provided they are stable (without evidence of progression by imaging for at least four weeks prior to the first dose of trial treatment and any neurologic symptoms have returned to baseline), have no evidence of new or enlarging brain metastases, and are not using steroids for at least 7 days prior to trial treatment. This exception does not include carcinomatous meningitis, which is excluded regardless of clinical stability.
7. Uncontrolled hypertension (systolic pressure >140 mm Hg or diastolic pressure > 90 mm Hg [NCI-CTCAE v5.0] on repeated measurement) despite optimal medical management.
8. Active of clinically significant cardiac disease including:
 - a. Congestive heart failure New York Heart Association (NYHA) $>$ Class II. (Appendix D)
 - b. Active coronary artery disease (CAD)
 - c. Cardiac arrhythmias requiring anti-arrhythmic therapy other than beta blockers or digoxin.
 - d. Unstable angina (anginal symptoms at rest), new-onset angina within 3 months before randomization, or myocardial infarction within 6 months before randomization.
9. Has history of (non-infectious) pneumonitis that required steroids or current pneumonitis.
10. Has an active infection requiring systemic therapy.
11. Evidence or history of bleeding diathesis or coagulopathy
12. Patient with any pulmonary hemorrhage/bleeding event of NCI-CTCAE v5.0 \geq Grade 2 within 4 weeks before initiating study treatment; any other hemorrhage/bleeding event of NCI-CTCAE v5.0 \geq Grade 3 within 4 weeks before initiating study treatment.

13. Patient with thrombotic, embolic, venous, or arterial events, such as cerebrovascular accident (including transient ischemic attacks) within 6 months of informed consent.
14. Presence of a non-healing wound, non-healing ulcer, or bone fracture.
15. History of organ allograft (including corneal transplant).
16. Known or suspected allergy or hypersensitivity to any of the study drugs (sorafenib, and or vemurafenib) study drug classes, or excipients of the formulations given during the course of this trial.
17. All patients with known diagnosis of Neurofibromatosis Type 1 or other known RAS-opathies
18. Patients with uncontrolled seizures
19. Treatment with medications that have known risk of QTc interval prolongation or Torsades de Pointe (TdP) within 14 days or 5 half-lives before dose of either drug is given in this study and for the duration of the study. Refer to Appendix E1 for medications with a known risk of TdP.
20. Treatment with a strong or moderate CYP3A inducers (e.g, phenytoin, carbamazepine, phenobarbital, St. John's Wort [*hypericum perforatum*], dexamethasone at a dose of greater than 16 mg daily, or rifampin [*rifampicin*], and/or rifabutin) or inhibitors within 28 days before dose of either drug is given in this study and for the duration of the study. Refer to Appendix G.
21. Malabsorption or other significant bowel or stomach resections
22. Has a history or current evidence of any condition, therapy, or laboratory abnormality that might confound the results of the trial, interfere with the patient's participation for the full duration of the trial, or is not in the best interest of the patient to participate, in the opinion of the treating investigator.
23. Has known psychiatric or substance abuse disorders that would interfere with cooperation with the requirements of the trial.
24. Inability to comply with the protocol and/or not willing or not available for follow-up assessments required to assess toxicity

Statistical Methods:

Between 7 and 12 evaluable patients total will be entered into this study. To obtain that number of evaluable patients we estimate up to 24 patients will possibly be enrolled. An evaluable patient is defined as one that receives at least one dose of doses of both agents (vemurafenib + sorafenib) and has a scan after at least 2 cycles of treatment.

After the adjustment based upon the NTF from May 13, 2022, we will examine 5 more patients at a reduced dose. If at least one patient of the five demonstrated a partial response (overall response rate of $\geq 20\%$), we will proceed with enrolling 7 more patients. Simon's two-stage design (Simon, 1989) will be used. The null hypothesis that the true response rate is 0% will be tested against a one-sided alternative. In the first stage, n=5 patients will be accrued. If there are zero patients with a response (either a PR or CR) in these 5 patients, the study will be stopped. Otherwise, 7 additional patients will be accrued for a total of 12. The null hypothesis will be rejected if 3 or more patients have a response (either PR or CR) in 12 patients.

Table of Contents

1. BACKGROUND AND RATIONALE.....	21
1.1. Disease Background and Introduction	21
1.2. Rationale of Clinical Trial	22
1.3. Study Agent(s) Background and Associated Known Toxicities	22
1.3.1. Vemurafenib	22
1.3.2. Sorafenib	23
1.4. Clinical Experience with Reported Phase I Trial with Vemurafenib + Sorafenib 23	
2. HYPOTHESIS	24
3. STUDY OBJECTIVES	24
3.1. Primary Objectives	24
3.2. Secondary Objectives	24
3.3. Exploratory Objectives	25
3.4. Endpoints	25
3.4.1. Primary Endpoint	25
3.4.2. Secondary Endpoint	25
3.4.3. Exploratory Endpoint	25
4. STUDY POPULATION	25
4.1. Inclusion Criteria	25
4.2. Exclusion Criteria	26
5. STUDY TREATMENT	28
5.1. Treatment Dosage and Administration	28
5.2. Administration of Vemurafenib + Sorafenib	28
5.3. Toxicities and Dosing Delays / Dose Modifications	29
5.3.1. Vemurafenib Dose Modifications	29
5.3.2. Sorafenib Dose Modifications	Error! Bookmark not defined.
5.4. Concomitant Medications / Treatments	32
5.5. Concomitant Therapies Requiring Caution	33
5.5.1. Vemurafenib	33
5.5.2. Sorafenib	33
5.6. Duration of Therapy	34
5.7. Duration of Follow-up	34

5.8.	Removal of Subjects from Protocol Therapy	34
5.9.	Subject Replacement	34
6.	STUDY PROCEDURES	35
6.1.	Screening / Baseline Procedures	35
6.2.	Optional Tissue Collection	36
6.3.	Procedures During Treatment (Cycle is 28 Days)	36
6.3.1.	Day 1 of Each Cycle	36
6.3.2.	Day 3 (Cycle 1 Only)	Error! Bookmark not defined.
6.3.3.	Days 8, 15 and 22 of Each Cycle	37
6.3.4.	Tumor Assessments Every 2 Cycles (Every 8 Weeks)	37
6.4.	Off Treatment Visit – to be Completed 14-28 (+/-2) Days From the Last Dose of Study Treatment	37
6.5.	Follow-up Procedures	38
6.6.	Study Treatment Discontinuation	38
7.	MEASUREMENT OF EFFECT	39

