11.2. Sample Size and Accrual

Between 7 and 12 evaluable patients total will be entered into this study. To obtain that number of evaluable patients we estimate up to 24 patients will possibly be enrolled. An evaluable patient is defined as one that receives at least one dose of both agents (vemurafenib + sorafenib) and has a scan after at least 2 cycles of treatment. We are hoping for a disease control rate of $\geq 40\%$. Simon's two-stage design (Simon, 1989) will be used. The null hypothesis that the true response rate is 5% will be tested against a one-sided alternative. In the first stage, $n=7$ patients will be accrued. If there are zero responses in these 7 patients, the study will be stopped. Otherwise, 5 additional patients will be accrued for a total of 12. The null hypothesis will be rejected if 3 or more responses are observed in 12 patients. This design yields a type I error rate of 0.0188 and power of 0.9077 when the true response rate is 40%. (Jung et al, 2004).

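### The synopsis tests a null response rate of 0%, which one response disproves, so its 3-of-12 rule has no link to its hypothesis and no stated operating characteristics

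*Combined protocol and SAP*

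**What the plan says.** The second paragraph of Statistical Methods in the Trial Synopsis applies after the note of 13 May 2022 and governs patients treated at the reduced dose. It invokes Simon's two-stage design and sets the hypothesis: "The null hypothesis that the true response rate is 0% will be tested against a one-sided alternative". The boundaries follow. Stage 1 takes 5 patients, and the trial ends there if none of them has a PR or CR; with at least one such response, stage 2 brings the total to 12. The final decision is: "The null hypothesis will be rejected if 3 or more patients have a response (either PR or CR) in 12 patients". The paragraph names no alternative rate, no type I error and no power. The only rate besides 0% is 20% or more, written in brackets after the condition that at least one of the five patients has a partial response.

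Section 11.2 carries a different design: 7 patients, stop at zero responses, otherwise 5 more, reject at 3 or more of 12. There, "The null hypothesis that the true response rate is 5% will be tested against a one-sided alternative", the hoped-for result is a disease control rate of at least 40%, and the stated properties are type I error 0.0188 and power 0.9077 at 40%. The Number of Patients row of the synopsis also describes 7+5 on disease control. Section 11.3.4 keeps disease control as the primary analysis, and Section 11.4 stops on no disease control in the first 7 evaluable patients.

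**The concern.** A two-stage design is built from a null rate, an alternative rate, a type I error and a power. A null of exactly 0% cannot play its part. It says that a response is impossible, so one response settles the matter and no cutoff above 1 can be derived from it. The synopsis nevertheless requires 3 of 12 before rejecting. With 1 or 2 responses it would formally retain a hypothesis already shown to be false.

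This rule decides whether 7 more patients are enrolled and whether activity is declared. As written, rejection shows only that the rate is not literally zero, and the chance of a false or missed declaration at any realistic rate is undisclosed. A reader who looks for those figures finds only the ones in Section 11.2, which describe other stage sizes, another null and a target for another endpoint.

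**Working it through.** **Inputs.** Synopsis, Statistical Methods: n1 = 5, stop at 0; n2 = 7; reject at 3 or more of 12; null 0%. Section 11.2: n1 = 7, stop at 0; n2 = 5; reject at 3 or more of 12; null 5%; properties quoted at 40%.

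**Formula.** The trial rejects if the total is at least 3, unless stage 1 had no response. So

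P(reject | p) = P[Bin(12, p) ≥ 3] − (1 − p)^n1 × P[Bin(n2, p) ≥ 3].

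**Step 1: reproduce Section 11.2 (7+5).**
- p = 5%: 0.01957 − 0.69834 × 0.00116 = 0.01876. Stated: 0.0188.
- p = 40%: 0.91656 − 0.02799 × 0.31744 = 0.90767. Stated: 0.9077.

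Both agree, so the formula is the one the plan used and those figures belong to the 7+5 boundaries.

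**Step 2: the synopsis rule under its own null.** At p = 0, the chance of any response is 0. Hence P(total ≥ c) = 0 for every c ≥ 1, and the trial stops at stage 1 with probability (1 − 0)^5 = 1. Cutoffs of 1, 2 and 3 all have type I error 0, so the null gives no reason to choose 3. The higher cutoff only lowers the chance of rejecting. At a true 20%, a cutoff of 1 with the same stage 1 rule rejects with probability 1 − 0.8^5 = 0.672, against 0.393 for a cutoff of 3 (step 3).

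**Step 3: the synopsis rule (5+7) at non-zero rates.**

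| True PR/CR rate | P(≥3 of 12) | Stage 1 stop, (1−p)^5 | P(≥3 of 7) | P(reject) |
|---|---|---|---|---|
| 5% | 0.01957 | 0.77378 | 0.00376 | 0.0167 |
| 10% | 0.11087 | 0.59049 | 0.02569 | 0.096 |
| 20% | 0.44165 | 0.32768 | 0.14803 | 0.393 |
| 30% | 0.74718 | 0.16807 | 0.35293 | 0.688 |
| 40% | 0.91656 | 0.07776 | 0.58010 | 0.871 |

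For example, at 20%: 0.44165 − 0.32768 × 0.14803 = 0.44165 − 0.04851 = 0.393.

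**Reading.** The cutoff of 3 makes sense only against a non-zero null. As an assumption, a 5% null for PR/CR gives type I error 0.0167 and a 10% null gives 0.096. The synopsis specifies neither.

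**The case against.** The operating rule is complete: a site knows when to stop, when to continue and when the trial succeeds. Under an assumed 5% null the rule is conservative, so the cutoff itself does no harm. No printed figure is miscalculated either: 0.0188 and 0.9077 reproduce, and 1 of 5 is 20%. All of this stands. The fault lies in the hypothesis and the missing properties, not in the boundaries or the arithmetic.

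A reader might infer three stronger points, which the documents do not support.
- *The trial has only 39% power for its 20% target.* The 20% describes an observed 1 of 5 that opens stage 2. It is not a design alternative. The 39% is an illustration, not a shortfall against a promise.
- *Power has dropped from 0.91 to 0.87.* The synopsis paragraph states no power, so nothing there falls. The 0.91 is a property of the 7+5 design.
- *The rule has 87% power at the planned alternative.* The 40% in Section 11.2 is introduced as a disease control rate, which includes stable disease at 16 weeks, although that section then speaks loosely of responses. Nothing shows that 40% was meant for PR or CR alone.

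**Conclusion.** The point holds. A 0% null is refuted by any single response, its type I error is identically 0, and the 3-of-12 cutoff cannot be derived from it. These statements need no assumption. The synopsis paragraph also lacks an alternative rate, alpha and power, and those in Section 11.2 do not transfer, because stage sizes, null rate and target endpoint all differ.

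The size rests on an assumed null for objective response. With 5%, borrowed from Section 11.2, type I error is 0.0167. The chance of rejecting is 0.39, 0.69 and 0.87 at true PR/CR rates of 20%, 30% and 40%, with no claim that any of these is the sponsor's alternative. The rule is therefore usable once a sensible null is stated; at present none is.

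**What to change.** In the Statistical Methods row of the synopsis:
1. Replace the 0% null with a non-zero null rate for objective response (PR or CR), with its justification.
2. Name an alternative rate for the same endpoint. Do not present 40% as that alternative unless the sponsor confirms that it applies to PR/CR.
3. State the exact properties of the 5+7 boundaries at those rates. If 5% is adopted, type I error is 0.0167; read power from the table above for the chosen alternative.
4. Say that the 20% is the observed stage 1 threshold and not the design alternative.

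Then reconcile this paragraph with the Number of Patients row and Sections 11.2, 11.3.4 and 11.4 on endpoint, null rate and stage sizes, so that one design governs, or so that it is clear which patients each design covers.

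The cost is wording, plus open disclosure of modest power at lower response rates. If the sponsor names an alternative near 20%, the disclosed 0.39 would raise a separate question about sample size.

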3.4. Endpoints

3.4.1. Primary Endpoint

- Disease control rate (defined as CR+PR+SD x16 weeks) using RECIST criteria.

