11.4. Stopping Rules

The study can be stopped early based on the following criteria:

- Per PI or sponsor discretion
- If none of the first 7 evaluable patients have disease control (CR+ PR +SD at 16 weeks)

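### The current text carries two unreconciled two-stage designs (5+7 on PR/CR, and 7+5 on 16-week disease control) and does not say which one governs or which patients count

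*Combined protocol and SAP*

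**What the plan says.** **Synopsis, Statistical Methods.** After a note to file of May 2022, five more patients are to be examined at a reduced dose. These five form the first stage, with this futility rule: "If there are zero patients with a response (either a PR or CR) in these 5 patients, the study will be stopped". One or more responders opens a second stage of seven, which brings the total to 12. The hypothesis is "The null hypothesis that the true response rate is 0% will be tested against a one-sided alternative", and the final rule is "The null hypothesis will be rejected if 3 or more patients have a response (either PR or CR) in 12 patients". The paragraph gives no alternative, type I error or power. The same row opens by expecting 7 to 12 evaluable patients, although this rule can end the study at 5.

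**Synopsis, Number of Patients.** Seven evaluable patients come first. The study stops if none has CR, PR or stable disease at 16 weeks; otherwise five more are added.

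**Section 11.2.** The section hopes for a disease control rate of at least 40%, but its rule is worded in responses: "In the first stage, $n=7$ patients will be accrued. If there are zero responses in these 7 patients, the study will be stopped". Five more are then added, and a 5% null is rejected at 3 or more of 12. The stated type I error is 0.0188 and the power is 0.9077 at 40%.

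**Section 11.4.** The only numerical stopping criterion is "If none of the first 7 evaluable patients have disease control (CR+ PR +SD at 16 weeks)".

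**Primary endpoint.** Section 3.4.1 gives "Disease control rate (defined as CR+PR+SD x16 weeks) using RECIST criteria". Sections 3.1 and 11.3.4 agree. Section 5.9 replaces patients in order to reach 7 evaluable.

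**The concern.** The two designs differ in first-stage size (5 or 7), second-stage size (7 or 5), endpoint (PR/CR, or CR+PR+SD at 16 weeks) and null rate (0% or 5%). They share only the total of 12 and the cut-off of 3. Stable disease at 16 weeks is a success under one and a failure under the other.

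Both are written as current, forward-looking rules; neither sits in an amendment log. The reduced dose has been carried into Sections 1.4 and 5.1, but Sections 5.9, 11.2 and 11.4 still work with 7 patients and do not mention the 5+7 rule.

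The interim decision, the final claim and the meaning of 3 of 12 are all at stake. The trial is open label. If the governing rule were chosen after outcomes are seen, the type I error would not be controlled. Section 12.10.1 also asks the data safety and monitoring committee to judge whether endpoints are being met, without a settled decision endpoint to judge against.

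**Working it through.** **Inputs.** From the synopsis: 5+7, stop at 0 of 5, reject at 3 or more of 12, null 0%. From Section 11.2: 7+5, stop at 0 of 7, reject at 3 or more of 12, null 5%, alternative 40%. The PR/CR rate is assumed at 0%, 5%, 10% and 20%, because the documents give no expected rate. The 20% value is the only response rate that the 5+7 paragraph names, and there it is an observed threshold (1 of 5).

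**Formula.** With first-stage size n1 and second-stage size n2 = 12 − n1:

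P(reject) = P(Bin(12, p) ≥ 3) − (1 − p)^n1 × P(Bin(n2, p) ≥ 3)

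P(early stop) = (1 − p)^n1

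**Step 1: reproduce Section 11.2 (7+5).**
- p = 5%: 0.01957 − 0.6983 × 0.00116 = 0.0188.
- p = 40%: 0.91656 − 0.02799 × 0.31744 = 0.9077.

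Both stated figures reproduce.

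**Step 2: 5+7 at the same rates.**
- p = 5%: 0.01957 − 0.7738 × 0.00376 = 0.0167.
- p = 40%: 0.91656 − 0.07776 × 0.58010 = 0.8714.

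The error rates in Section 11.2 therefore do not describe the synopsis rule.

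**Step 3: 5+7 at its own null.** At p = 0% no response can occur. The rule stops with probability 1 and the type I error is 0 for any cut-off of one or more. A single response already refutes the null, so requiring 3 of 12 has no error-rate basis in that paragraph.

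**Step 4: a case where the rules split.** Suppose none of the first five patients has PR or CR and one has stable disease at 16 weeks. The 5+7 rule stops the study. The futility boundary in Section 11.4 cannot then be met.

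**Step 5: how often they split.** Assume that both rules judge the same patients, that PR/CR is a subset of disease control, and that true disease control is 40%. No disease control in 7 implies no PR/CR in the first 5, so

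P(5+7 stops, 7-patient boundary not met) = (1 − q)^5 − 0.6^7, where q is the PR/CR rate and 0.6^7 = 0.0280.

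| q (assumed) | (1 − q)^5 | Split at the interim | Final success, 5+7 on PR/CR | Final success, 7+5 on disease control |
|---|---|---|---|---|
| 0% | 1.000 | 0.972 | 0 | 0.908 |
| 5% | 0.774 | 0.746 | 0.017 | 0.908 |
| 10% | 0.590 | 0.562 | 0.096 | 0.908 |
| 20% | 0.328 | 0.300 | 0.393 | 0.908 |

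**The case against.** The best defence is that the rules are sequential. The 5+7 paragraph speaks of five more patients at a reduced dose, so it may be a later rule for a new cohort, with 7+5 left over from the starting dose used before. The note to file is not among the documents and might settle this. The reading is plausible, and it makes the same-patients assumption in Step 5 an assumption, not a fact. But no passage says that 5+7 replaces 7+5, and none says whether patients treated before the dose change count toward 5, 7 or 12. If replacement was meant, the decision endpoint changed in one paragraph and nowhere else, which also needs repair.

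A reader might infer several stronger points that the documents do not support:

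- *That efficacy results drove the change of rule.* Section 1.4 attributes the dose change to toxicity in the first three patients. The loss of error control is conditional on a later choice.
- *That an early stop under 5+7 would leave the primary endpoint unaddressed.* Section 11.3.4 keeps disease control as the primary efficacy analysis; an early stop would leave it imprecise.
- *That Section 11.2 explicitly stops on disease control.* Its stopping sentence says responses. The disease-control meaning comes from its lead-in, and is explicit only in Section 11.4 and the Number of Patients row.
- *That 0.972 is the chance of continuing under 7+5 at 40% disease control.* Section 11.4 also allows stopping at the discretion of the principal investigator or sponsor, so it is only the chance that the futility boundary is not met.

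**Conclusion.** The contradiction stands and must be resolved before either rule is applied. The current text holds two two-stage designs with different stage sizes, endpoints and nulls, and gives no statement of precedence. Only 7+5 comes with an alternative, type I error and power, and those figures are correct for it.

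The size of the practical conflict depends on the true PR/CR rate. Under the assumptions in Step 5, the rules disagree at the interim with probability 0.300 even at a PR/CR rate of 20%, and more often at lower rates. If the rules were meant for separate cohorts, these probabilities do not apply as they stand. The defect is then an incomplete update, with the endpoint and the countable patients left undefined.

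**What to change.** State one governing design identically in both synopsis rows and in Sections 3.4.1, 5.9, 11.2 and 11.4. Give the endpoint, stage sizes, null, alternative, type I error and power, and say which patients count toward each stage, including those treated before the dose change.

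To match the stated primary endpoint, base the decision on 16-week disease control with a 5% null and a 40% alternative. Either split is workable:

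- 7+5: type I error 0.0188, power 0.9077.
- 5+7: type I error 0.0167, power 0.8714.

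Report PR/CR descriptively, and replace *response* with *disease control* in Section 11.2.

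If the sponsor intends PR/CR as the decision endpoint, amend the primary endpoint everywhere and give a non-zero null and an alternative, with the type I error and power that follow.

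The cost is a text amendment. Keeping the 5+7 split on disease control lowers power from 0.91 to 0.87. The change cannot be called free of extra patients, because total enrolment depends on whether earlier-dose patients count.
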